### **9.4 Interim Analyses and Stopping Rules**

Interim analyses are not included in our protocol and will not be necessary to assess our study aims.

The study will be stopped prior to its completion if: (1) the intervention is associated with adverse effects that call into question the safety of the intervention; (2) difficulty in study recruitment or retention will significantly impact the ability to evaluate the study endpoints (in this case, the trial will be suspended versus stopped completely to allow assessment and modification of recruitment procedures); (3) any new information becomes available during the trial that necessitates stopping the trial; or (4) other situations occur that might warrant stopping

the trial. MPI [name] will include an assessment of external information that might impact the viability of the trial in the annual progress report to NIH and will consult with the IMC to assess the impact of significant data loss due to problems in recruitment, retention, or data collection.

The IMC members are [name], [name], and [name]. [name] is a biostatistician, Drs. [name] and [name] are clinical psychologists with combined experience with clinical trials, mindfulness-based interventions, and adaptations of clinical protocols for underserved and high stress populations. The IMC is composed to ensure that the safety of study subjects is protected while the scientific goals of the study are being met.

The IMC members will not be associated with this research project, are not part of the key personnel involved in this grant, and have not collaborated with the two MPIs, Drs. [name] and [name], within the past 3 years. Written documentation attesting to absence of conflict of interest will be collected at least annually, and each time there is a change in site investigators and/or institutions involved in the study. Thus, the IMC will be able to work independently of the MPIs. The members of the IMC will be qualified to review the patient safety data generated by this study.

The IMC will serve in accordance with the guidelines set forth in a charter provided to each member. IMC members will review and agree to the charter at the initial meeting. If changes to the charter are necessary, the IMC will review and affirm their agreement with the changes. Their concurrence will be noted in the IMC meeting summary. The IMC will typically meet twice a year, or as deemed necessary. A quorum of more than half of the IMC members is required to convene a meeting of the IMC. The IMC will approve the final protocol of the study before the study begins enrolling participants. In monitoring the data and safety throughout the trial, the IMC may recommend continuation of the trial, modifications to the trial, or termination of the trial in the event of overwhelmingly significant efficacy difference between groups or unacceptable adverse events.

Study progress and safety will be reviewed monthly (and more frequently if needed). Progress reports, including participant recruitment, retention/attrition, and AEs will be provided to the IMC members following each of the quarterly reviews. An Annual Report will be compiled and will include a list and summary of AEs. In addition, the Annual Report will address: (1) whether AE rates are consistent with pre-study assumptions; (2) reason for dropouts from the study; (3) whether all participants met entry criteria; (4) whether continuation of the study is justified on the basis that additional data are needed to accomplish the stated aims of the study; and (5) conditions whereby the study might be terminated prematurely. The Annual Report will be sent to the IMC and will be forwarded to the IRB and NCCIH. The IRB and other applicable recipients will review progress of this study on an annual basis.

The study team will generate annual Study Reports for the IMC and will provide information on the following study parameters: recruitment, retention, enrollment by month, demographics, subject status, treatment duration, and AE status. Study Report tables will be generated only from aggregate (not by group assignment) baseline and aggregate safety data for the study population. A separate Closed Safety Report, with unmasked group baseline and safety data, will be generated for the IMC by a designated unmasked member of the team, but

will not be reviewed by the study team. As noted above, we will also review quarterly with the IMC subject accrual, subject status, adherence data, AEs and SAEs.

During the funding of this study, any action by the IRB or one of the study investigators that results in a temporary or permanent suspension of the study will be reported to the NCCIH Program Official within one business day of notification.

## **9.5 Outcomes**

Outcomes will be analyzed using quantitative analyses (sensitivity and responsiveness) after creating composite scores for self-report measures and physiological outcomes. For behavioral data, we will analyze individual behavioral items as well as a composite score.

Committee oversight of outcome analyses and results is not included in our protocol (oversight of AE information is discussed above in section 9.4). However, Drs. [name] (Portland) and [name] (Albuquerque) will review all data collection forms on an ongoing basis for data completeness and accuracy as well as protocol compliance. The primary source of research materials will be a combination of self-report (i.e., psychological resilience, trauma, alcohol misuse, depression, suicidality, burnout, and aggression), physiological (C-RP, IL-6, IL-10, TNF- $\alpha$ ), and behavioral (use of force reports, e.g. BlueTeam database) outcomes. Self-report measures will be collected via Qualtrics; psychophysiological data will be collected via a dried blood spot kit; and audio homework assignment data will be collected via Ilumivu; and study forms will be entered by the research team and stored electronically on REDCap. Behavioral data will be obtained from the database with the assistance of police department staff. Drs. [name] (Portland) and [name] (Albuquerque) will oversee data downloads from Qualtrics, REDCap, and Ilumivu as well as psychophysiological and behavioral data collection; a second research team member will verify that data downloads and collection were done correctly. The project manager will manage data storage.

### **9.5.1 Primary Outcome**

Given that our goal is to optimize study procedures and outcome measurement through sensitivity and responsiveness analyses, we will not be grouping outcome measures into primary and secondary categories. The data we obtain through this trial will be used to identify primary and secondary outcomes for a future fully-powered efficacy RCT.

### **9.5.2 Secondary Outcomes**

Given that our goal is to optimize study procedures and outcome measurement through sensitivity and responsiveness analyses, we will not be grouping outcome measures into primary and secondary categories. The data we obtain through this trial will be used to identify primary and secondary outcomes for a future fully-powered efficacy RCT.

## **9.6 Data Analyses**

### Quantitative:

Following best practice guidelines including CONSORT feasibility guidelines and past research, we will measure sensitivity (using a relative efficiency approach) and

responsiveness to change (examining within-group change over time). Relative efficiency analyses will be used to establish that our outcome measures are sensitive to differences between our treatment arm of focus (MBRT) and our other two arms - an active control arm (SME) and a no-treatment control arm (NIC). Therefore, sensitivity analyses will focus on assessing the degree to which outcomes are sensitive to study arms and not whether change is significant. Sensitivity to differences for MBRT compared to SME and NIC will be assessed by examining the relative efficiency of each outcome variable for MBRT versus SME and NIC separately. We will calculate the relative efficiency for MBRT versus SME by conducting one-way, between-subjects Analysis of Covariance (ANCOVA) analyses with MBRT versus SME as the independent variable and each outcome variable at post-training as the dependent variable; we will include study site and gender as covariates. We will also conduct ANOVAs using the same independent and dependent variables to ensure that all inferential tests are conducted and identify any potential Type II Errors among the ANCOVAs. We will then divide the *F*-statistic for each behavioral (BlueTeam/departmental use of force; individual indicators of use of force as well as a composite score of use of force using the individual indicators), physiological (C-RP, IL-6, IL-10, TNF- $\alpha$ ), and self-report (aggression, alcohol misuse, depression, suicidal ideation, trauma symptoms, burnout, and psychological resilience) outcome by the largest *F*-statistic among these analyses, such that the larger the number, the more sensitive that outcome is to the impact of MBRT relative to the active control group.

To calculate the relative efficiency of MBRT versus NIC, we will conduct one-way, between-subject ANCOVAs with MBRT vs. NIC as the independent variable, each outcome variable at post-training as the dependent variable, and gender and study site as covariates. Again, we will also conduct ANOVAs using the same independent and dependent variables to ensure all inferential tests are conducted and identify any potential Type II Errors among the ANCOVAs. We will then divide the *F*-statistic for each behavioral, physiological, and self-report outcome by the largest *F*-statistic among these analyses; again, the larger the number, the more sensitive the outcome is to MBRT relative to the no-treatment control group. These sensitivity analyses will allow assessment of which behavioral, physiological, and self-report outcomes are most sensitive to MBRT.

Responsiveness to change across time will be assessed in the MBRT arm for behavioral, physiological, and self-report outcomes by: 1) calculating and comparing standardized mean responses (SMR) for outcomes by subtracting the baseline mean response for each outcome from the post-intervention mean response for that outcome, and dividing by the standard deviation of change for that outcome; 2) calculating and comparing partial correlation coefficients (adjusting for study site and gender) between a global impression of change measure that captures the subjective experience of changes in stress, job performance, and resilience at post-intervention and residualized change scores (baseline to post-intervention) for each self-report outcome. For both SMR values and correlation coefficients, the higher the absolute value, the more responsive the outcome is to change across time in the MBRT arm. We will conduct additional correlation analyses using the same variables without adjusting for study site and gender to identify any potential Type II Errors among the partial correlations.

In addition, we will examine data for any indications of systematic site differences. Using baseline data (where sample size will be greatest) and pooling arms, since no treatment differences are expected at baseline, distributions of standardized responses on outcome measures will be summarized, graphed, and compared across sites. Key parameters, reliability

estimates (i.e., Cronbach's alpha), and intraclass correlations will be estimated and checked for discrepancies between sites. Identified discrepancies will be investigated to determine site-specific issues that would undermine assumptions of conceptual and structural equivalence of measurement.

Given the optimization aim of our study, our analyses will not adjust for intraclass correlations across study arms (and any heterogeneity in those correlations). Our study will allow us to obtain information about the magnitude of intraclass correlations and the degree to which they are heterogeneous across study arms, which we will use for our data analysis plan in a future fully-powered efficacy RCT.

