#### **Objective 4: Assess participant experience and optimize outcome measures across sites.**

Well-developed content themes with data saturation emerging from feedback interviews will provide information on acceptability, impact of assessments, protocol and intervention fidelity, and equivalence of these markers across sites. Benchmark sensitivity and responsiveness values will determine the most sensitive and responsive measures relative to all study outcomes, versus a significance testing approach in which standardized/conventional threshold values are used to make decisions regarding significance. Sensitivity and responsiveness information will determine which outcomes are most impacted by MBRT for retention in a future full-scale multi-site efficacy trial. Benchmarks for equivalence across sites will be evidenced by: a) qualitative themes that suggest experiential continuity across sites, and b) equivalence in outcome measure response distributions, reliability estimates, and intraclass correlations.

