to obtain more accurate (i.e., unbiased)  $F$ -values, we will include study site and gender, as covariates in all ANOVA analyses (i.e., perform a one-way between-subjects Analysis of Covariance for each outcome). Assessing relative efficiency entails generating  $F$ -values for comparison purposes and does not require determining whether the group differences are significant; however, adjusting for non-ignorable clustering will allow us to avoid deviation from a type I error rate of .05 and calculate  $F$ -values that most precisely reflect group differences for each outcome. Responsiveness to change will be assessed, in part, by comparing standardized mean responses, which will not require conducting an inferential test and therefore will not be impacted by type I or type II error rates. To assess responsiveness to change, we will also calculate partial correlations with a global impression of change measure and residualized change scores for each self-reported outcome, adjusting for variability due to gender and study site. Just as for our relative efficiency assessment, examination of partial correlations will not entail significance testing, but instead generating correlation coefficients for comparative purposes; however, we will partial out variability due to gender and study site to obtain precise (i.e., unbiased) estimates of covariance between a global impression of change measure and self-report outcomes.

Based on our recent R21 study (R21AT008854), in which we had an overall attrition rate of 20% across all study arms, we predict an overall attrition rate of 20% across our three study arms.

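### Dividing each F by the largest F can rank the outcomes, but it cannot establish that any of them is sensitive to MBRT, because the top score is 1.0 for any data

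*Combined protocol and SAP*

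**What the plan says.** Section 9.6 (Quantitative) gives the purpose of the sensitivity analysis: "Relative efficiency analyses will be used to establish that our outcome measures are sensitive to differences between our treatment arm of focus (MBRT", followed by the names of the other two arms. For MBRT versus SME, and separately for MBRT versus NIC, an ANCOVA with site and gender as covariates is run on each post-training outcome. The plan then divides the F for each "outcome by the largest *F*-statistic among these analyses". The reading rule is "such that the larger the number, the more sensitive that outcome is to the impact of MBRT" against SME and, for the other comparison, "the larger the number, the more sensitive the outcome is to MBRT relative to the no-treatment control group".

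No minimum F, effect size or interval is attached to the ratio. Section 9.6 adds "Therefore, sensitivity analyses will focus on assessing the degree to which outcomes are sensitive to study arms and not whether change is significant", and section 9.2 says that relative efficiency "does not require determining whether the group differences are significant".

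Section 1.1, Objective 4, sets the benchmark: "Benchmark sensitivity and responsiveness values will determine the most sensitive and responsive measures relative to all study outcomes". It also states the use: "Sensitivity and responsiveness information will determine which outcomes are most impacted by MBRT for retention in a future full-scale multi-site efficacy trial". The Précis (item 4.2) speaks of confirming sensitivity. Section 9.1 says that the sensitivity of the use-of-force measure to group differences has, to the investigators' knowledge, not yet been assessed.

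**The concern.** Whether a measure responds to MBRT at all is an absolute question. Which measure responds most is a relative one. The ratio answers only the second, while section 9.6, item 4.2 and the use-of-force aim in section 9.1 also raise the first.

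If MBRT and SME do not differ on anything, the planned table still shows one outcome at 1.0 and several others not far behind. The sign is lost as well: with two arms F is the square of t, so an outcome on which MBRT did worse scores the same as one on which it did equally better. A team choosing efficacy-trial outcomes could carry forward a measure on which nothing happened, or on which the change was in the wrong direction, with nothing in the index to warn them.

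**Working it through.** **Inputs from the protocol.** 104 participants at 2:1.5:1 (Précis; section 3); predicted attrition 20% (section 9.2); site and gender as covariates (section 9.6). The outcomes listed for the ratio are 7 self-report constructs, 4 biomarkers, one use-of-force composite and an unstated number of use-of-force indicators.

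**Assumed.** 12 outcomes (7 + 4 + 1), with 16 as the upper case; normal outcomes with common correlation 0.3 (range 0 to 0.5); no true arm difference on any outcome.

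**1. The plan's own figures.** 104 × 2/4.5 = 46.2, 104 × 1.5/4.5 = 34.7 and 104 × 1/4.5 = 23.1, against the stated 47, 35 and 22: each within two participants. After 20% attrition: 47 × 0.8 = 37.6, 35 × 0.8 = 28.0 and 22 × 0.8 = 17.6, so about 38, 28 and 18.

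**2. The identity.** RE_j = F_j / max(F). For the outcome with the largest F, RE = 1 whatever that F is. Multiplying every F by a constant changes no ratio: F-values of 40, 20 and 10 give 1.0, 0.5 and 0.25, and so do 0.4, 0.2 and 0.1. This needs no assumption about the data.

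**3. What is discarded.** Simulated ANCOVAs, 38 v 28, 12 outcomes, correlation 0.3:

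| True difference | Top RE | Median largest F | Mean number of outcomes with RE ≥ 0.5 |
|---|---|---|---|
| 0 on every outcome | 1.0 always | 3.5 | 2.5 |
| 0.5 SD on every outcome | 1.0 always | 11.5 | 4.0 |

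The lower ratios shift somewhat, but the quantity that separates the two cases is the size of F, and the division removes it.

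**4. What the top outcome looks like by chance.** With no effect, the median largest F is about 3.44 (38 v 28) and 3.45 (38 v 18). From d = √(F × (1/n₁ + 1/n₂)):

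- v SME: √(3.44 × (1/38 + 1/28)) = √(3.44 × 0.0620) = 0.46 SD
- v NIC: √(3.45 × (1/38 + 1/18)) = √(3.45 × 0.0819) = 0.53 SD

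These runs had no covariates. With site and gender included, the median largest F is 3.50 and 3.46, and the median d is 0.47 and 0.53. Over 12 to 16 outcomes and correlations 0 to 0.5, the range is 0.43 to 0.52 SD v SME and 0.49 to 0.59 SD v NIC. As a check, for 12 independent outcomes the exact median of the largest F on 1 and 61 df is 3.79; the simulation gives 3.80.

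**5. What an interval would add.** Approximate 95% half-widths are 1.96 × √0.0620 = 0.49 and 1.96 × √0.0819 = 0.56. The median chance winner would be reported as 0.46 (−0.03 to 0.95) v SME or 0.53 (−0.03 to 1.09) v NIC. A reader sees at once that no difference is not excluded. From the ratio alone the reader sees 1.0.

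**The case against.** The strongest reply is that the plan never meant the index as proof. The sentence after the disputed one limits the aim to the degree of sensitivity; section 9.2 says the F-values are for comparison; Objective 4 makes the benchmarks relative to the other outcomes and deliberately avoids significance thresholds. Section 9.1 proposes no efficacy hypotheses. Ranking by relative efficiency is legitimate, and raw F-values will exist because no ratio can be formed without them. Section 9.1 also plans means and confidence intervals.

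Most of that stands, and it rules out several stronger readings that a reader might infer:

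- *That the benchmark values were left out by oversight.* They are relative by design.
- *That the plan runs no tests or absolute measures.* ANCOVAs and ANOVAs are both run, and standardized mean responses are not scaled to a maximum. Those responses are, however, computed within the MBRT arm only and cannot show a between-arm difference.
- *That the SME and NIC ratios are wrongly compared with each other.* The plan treats the two comparisons separately.
- *That this ranking alone picks the future outcomes.* Responsiveness is used with it, item 4.2 adds psychometric soundness, and section 9.6 checks self-report sensitivity against qualitative reports.
- *That the normalization produces the 0.46 and 0.53 SD.* It does not. They come from taking the largest of 12 chance results and would be the same with no division.

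What the reply does not remove is that the stated purpose is stronger than a ranking can support, and that no section links the raw F-values or intervals to how the ranking is read or which outcomes are kept.

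**Conclusion.** The point holds as a mismatch between claim and index. The top relative efficiency is 1.0 with certainty, by algebra, so the analysis can rank outcomes but cannot establish sensitivity, and it ignores direction. The size of what may go unseen, a median of about 0.46 SD v SME and 0.53 SD v NIC with no true effect, rests on the assumed 12 outcomes, correlation 0.3, normality and 20% attrition, and describes chance rather than the division.

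A reader might go further and infer that no outcome should be called sensitive unless the largest F beats a permutation threshold. The documents do not support that. Objective 4 sets significance rules aside, and section 9.2 reports no power calculation. At an assumed 5% cutoff (95th percentile of the largest null F about 8.6 v SME and 8.7 v NIC; 12 outcomes, correlation 0.3, no covariates), a trial with one true difference of 0.5 SD would pass in only about 22% of cases v SME and 16% v NIC. Such a gate would usually discard the real signal.

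**What to change.** 1. In section 9.6, change the stated purpose from establishing that the measures are sensitive to ranking them by sensitivity, and align item 4.2 of the Précis.
2. Beside each relative efficiency, report the raw F and the signed standardized mean difference, adjusted for site and gender, with its 95% CI.
3. State that the ranking is read with these quantities, including direction, when outcomes are considered for retention.
4. Optionally, show where the largest F falls in its distribution when arm labels are permuted within site-by-gender strata. Present it as descriptive context only, not as a rule for calling outcomes sensitive or dropping them. Section 9.6 leaves within-group correlation unadjusted, so the reference reflects no effect of any kind, group effects included.

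The cost is a few lines of text and a short program on data already being collected; conduct and sample size do not change. The downside is that the report may show the top-ranked outcome's interval including no difference. The intervals also do not correct for selecting the largest result: under the assumptions above, the largest F exceeds its ordinary 5% critical value in about 40% of no-effect trials in either comparison. They should therefore be shown for every outcome, not only the winner.
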